For the dog study, beagle dogs were exposed to aerosolized xylitol for varying durations (high exposure group at 1 hour, mid exposure group at 0.5 hours, and low exposure group at 0.25 hours). A control group was exposed for 1 hour to a nebulized normal saline solution. Mean xylitol aerosol concentrations were 3.49 ± 0.15 mg/L for the high exposure group, 3.55 ± 0.18 for the mid exposure group, and 3.54 ± 0.18 for the low exposure group. Mean particle sizes of xylitol were determined to be in the inhalable size range for dogs [(actual range 2–3) μm mass median aerodynamic diameter]. Mean total inhaled doses were estimated as 105, 53, and 27 mg/kg, for the high, mid, and low exposure groups, respectively. Mean total deposited doses to the pulmonary region were estimated as 21, 11, and 5 mg/kg, for the high, mid, and low exposure groups, respectively.

All dogs survived to the scheduled necropsy and xylitol exposures were generally well-tolerated. No treatment-related findings were observed in clinical signs, body

weights, physical (with ECGs) and ophthalmic examinations, food consumption, clinical pathology, gross pathology, organ weights, or histopathology. The No Observed Effect Level (NOEL) was determined to be the high exposure level.

In this pilot study we propose to test the hypothesis that aerosolized hypertonic xylitol given twice daily for 2 weeks, will be safe and well tolerated and potentially lower the density of colonization in subjects with CF compared to hypertonic saline. We chose hypertonic concentration of xylitol to be comparable in part to hypertonic saline which is being offered as a routine treatment in hospitalized patients with CF exacerbation. In addition, hypertonic concentration allows us to deliver adequate amounts of xylitol with twice a day dosing which will help with compliance.

Protocol

Randomized Controlled Study of Aerosolized hypertonic xylitol versus hypertonic saline in hospitalized patients with exacerbation of cystic fibrosis

The study has been approved by the University of Iowa Institutional Review Board as well as the Food and Drug Administration. This will be a randomized, controlled study. Blinding is not assured because of ability to taste the sweetness of xylitol.

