First dose pre and post spirometry: All subjects will undergo spirometry before and 20 minutes after the first study drug dose as follows.

Perform baseline spirometry and measure SpO₂. Multiply the patient's best FEV₁ by 0.80 to obtain 20% fall in FEV₁ value.

Premedicate subject with 4 puffs albuterol and wait 15-30 min.

Begin study drug nebulization.

Wait for 15-30 minutes and repeat spirometry and SpO₂.

Subject is excluded from the study if SpO₂ is <89% or FEV₁ declines by 20% or greater from baseline.

Administration: Subjects will take their routine inhaled medicines followed by chest physical therapy. All subjects will then receive 2-4 puffs of albuterol metered dose inhaler 15-30 minutes before the study drug. Finally the study drug will be inhaled. All empty, unused and partially used study drug containers will be tracked by the investigators. Subjects will be required not to use any new treatments if not medically indicated during the study period.

Day 14 follow-up: Subjects will undergo spirometry and sputum collection and answer CFQ-R questionnaire. Blood draw for LFTS and electrolytes will be done if not done for clinical reasons. If subjects are discharged prior to 14 days of xylitol use, nebulizer solutions will be sent home. They will be asked to keep a log of nebulizer use and bring back empty and unused vials on follow-up visit (Day 10-15, preferably day 14). They will undergo spirometry and sputum collection and questionnaire administration on that day. If subjects don't return on this day, they will have a phone follow-up for adverse events and compliance.

Phone follow-up: Week 1, Day 90 and Day 180 after discharge: Subjects will be contacted by phone at these time points to enquire about further pulmonary exacerbations, admissions, and other AEs.

In the event of bronchospasm: Subjects will alert the nurses or study team members. Nebulized bronchodilators will be immediately administered. Once symptoms resolve, they will undergo spirometry using a portable handheld spirometer by a trained user. If the subjects dropped FEV₁ by 20% or greater from their baseline, they will not receive further study drug. However, they will remain in the study for completion of data collection.

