Endpoints: Primary outcome will be FEV₁ change from baseline. Other safety assessments include vital signs within 30 minutes after nebulization, withdrawal from the study, rescue bronchodilator use, incidence of treatment related adverse events, and laboratory tests (chemistry and liver function tests). Efficacy outcomes include difference in density of colonization per gram of sputum from baseline to day 14, time to next hospitalization, difference in CFQ-R, sputum cytokine levels and cell counts.

Adverse events such as cough, chest tightness, and headache will be scored on a visual analog scale. Other variables collected include antibiotic and other medication use during the hospitalization, demographics, organ involvement with CF, genotype data from medical records. Follow-up phone calls will be made 1 week, 3 months and 6 months

after study completion for any complications and to assess the time to next hospitalization.

Adverse events: Any untoward medical occurrence (abnormal symptom, sign or laboratory value) in a study subject that is temporally associated with the study drug will be reported as an adverse event. The event does not have to have a causal relationship with the treatment. The event will be classified by the investigator as mild, moderate or severe. The relationship of an adverse event to the study drug will be determined by the investigator to be ‘unlikely to be related, possibly related, probably related or definitely related’.

Future Use of Stored Specimens

Subjects will be asked for permission to keep any remaining unlinked sputum and blood specimens for possible use in future research studies. Samples may be shared with other investigators at other institutions. The samples will not be sold or used directly for production of any commercial product. No human genetic tests will be performed on samples. Each sample will be labeled only with a study ID to protect subject’s confidentiality.

There are no benefits to subjects in the future research use of their specimens. Reports about future research done with these samples will not be kept in their health records.

Subjects can decide if they want their samples to be used for future research or have their samples destroyed at the end of the study. A subject’s decision can be changed at any time prior to the end of the study by notifying the study investigators in writing.

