However, if a subject consents to future use and some of their specimens have already been used for research purposes, the information from that research may still be used.

Statistical analysis: We plan to enroll a total of 60 subjects for this study. These subjects will be randomly assigned to the treatment (xylitol) and control (saline) groups, with a goal of 30 subjects in each group. Since this is a pilot safety study, it has been primarily powered to detect common adverse events. Assuming that the likelihood of a subject experiencing an adverse event is no less than 5%, a sample size of 30 subjects ensures 80% power towards event detection [16]. (In other words, with a group sample size of 30, the probability of observing at least one adverse event in the group is at least 80%.)

Study Performance

Accrual will be assessed on a monthly basis. We will examine the number of screened subjects, those meeting eligibility criteria, the number of persons consenting to participate and the number of randomized. The rate of accrual will be tracked versus the expected number to achieve the target of 60 participants randomized.

We will also track the completion number and proportion by time. The number of study terminations and reason for termination will be measured. The subject will undergo a spirometry and if the FEV₁ has declined by 20%, the subject will be terminated from the study.

Baseline

The composition of the study sample will be described in aggregate. Comparison of randomized participants of baseline characteristics will be analyzed using 2 sample t-test,

Wilcoxon rank sum test, and analysis of variance (ANOVA) as indicated by the type and characteristics of the variable.

Outcomes

To assess the adequacy of these group sample sizes for testing a trend in efficacy, we consider the outcome of log CFU. We assume an average density of colonization of 6.5 log CFU with a SD of 1.5 log CFU among CF subjects. To detect a reduction of 1.5 log CFU in the xylitol group with 80% power, the required sample size is 17 subjects per group. (This computation is based on a two-sided, two-sample t-test conducted at the 0.05 level of significance.) Data from all patients who have received at least one dose of the drug or placebo will be analyzed. Thus, the analysis will be based on intention to treat. All tests will be two-sided, and conducted using a significance level of 0.05.

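### Withdrawal from the study is listed as a safety measure, but permanent stopping of study drug is not; the withdrawal count depends on which retention rule is followed and can miss treatment-ending intolerance

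*Combined protocol and SAP*

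**What the plan says.** The primary outcome in Endpoints is change in FEV₁. The other safety measures include vital signs, laboratory tests and "withdrawal from the study, rescue bronchodilator use, incidence of treatment related adverse events". The hypothesis, at the end of Background, is that xylitol "will be safe and well tolerated" compared with hypertonic saline.

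Four places, besides the first-dose check, bear on what happens to a subject after a 20% FEV₁ fall:

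- First dose pre and post spirometry: "Subject is excluded from the study if SpO₂ is <89% or FEV₁ declines by 20% or greater from baseline".
- In the event of bronchospasm, after a fall of that size: "they will not receive further study drug. However, they will remain in the study for completion of data collection".
- Study Performance: "if the FEV₁ has declined by 20%, the subject will be terminated from the study". Risks gives the same rule, specifically for bronchospasm with the study drug.
- Stopping criteria: further exposures stop. Nothing is said about study status.

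Study Performance also records the number of terminations and their reasons. The Outcomes section applies Fisher's exact test to adverse events, compliance and rescue bronchodilator use, and a Poisson comparison to adverse-event counts. It names no analysis of withdrawals or of drug stops.

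**The concern.** Leaving the study and stopping the drug are different events, and the bronchospasm rule deliberately separates them. Only the first is a listed outcome. A subject permanently taken off drug for harm may not appear in it, while a subject who leaves for a reason unrelated to the drug does.

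In a pilot safety trial with an active comparator, the number of subjects in each arm who could not continue the drug is a basic tolerability result. As the plan stands, no listed outcome reports it. The withdrawal line could look balanced while drug is being stopped more often in one arm.

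**Working it through.** **1. The plan's own figure.** The only stated figure for detecting safety events is an 80% chance of at least one event in 30 subjects at a 5% rate. 1 − 0.95³⁰ = 1 − 0.215 = 0.785, which agrees with 80% to within 1.5 points. The point below does not depend on it.

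**2. Same fall, different status.**

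| Rule | Study drug | Study status | Counted as a withdrawal? |
|---|---|---|---|
| First-dose check | ends with exclusion | excluded | presumably yes |
| In the event of bronchospasm | stopped | remains in study | no, on the plain words |
| Study Performance; Risks | ends with termination | terminated | presumably yes |
| Stopping criteria | stopped | not stated | cannot be told |

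The last column is an inference, because the plan never defines withdrawal. The bronchospasm rule is not limited to doses after the first, so a first-dose bronchospasm with a 20% fall meets both of the first two rows.

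**3. Does reconciling the sections cure it?** Not by itself. If subjects are retained, the withdrawal count misses these drug stops, and better retention means more are missed. If they are terminated, the count includes them but mixes them with unrelated departures. A count defined on drug discontinuation has the same meaning either way. The denominator is already settled: Outcomes analyses everyone who received at least one dose, which includes first-dose exclusions.

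**4. Illustrative size.** The documents give neither a rate of drug-stopping falls (q) nor the share that a withdrawal count would capture (f), so both are assumed. If the retention rule is followed, f is roughly the share arising at the first-dose check. The expected count per arm is 30 × q × f, and the chance of at least one is 1 − (1 − qf)³⁰.

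| q | f = 0 | 0.25 | 0.5 | 0.75 | 1 |
|---|---|---|---|---|---|
| 5% | 0.00 | 0.31 | 0.53 | 0.68 | 0.785 |
| 10% | 0.00 | 0.53 | 0.79 | 0.90 | 0.96 |

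At q = 5%, the expected count is 30 × 0.05 = 1.5 per arm if every stop counts, and 1.5 × f otherwise.

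For a comparison between arms, the expected difference shrinks in proportion to f when f is the same in both arms. The exact power of a two-sided Fisher test at 0.05 with 30 per arm, by full enumeration, is:

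| Assumed stop rates | Difference, all counted | Power | Difference, half counted | Power |
|---|---|---|---|---|
| 20% vs 3% | 17 points | 34% | 8.5 points | 5% |
| 30% vs 5% | 25 points | 63% | 12.5 points | 16% |
| 40% vs 10% | 30 points | 71% | 15 points | 24% |

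**5. What the comparison can do at best.** With no stops on saline, 5 of 30 on xylitol gives p = 2 × C(30,5)/C(60,5) = 2 × 142,506/5,461,512 = 0.052. Six of 30 gives 2 × C(30,6)/C(60,6) = 2 × 593,775/50,063,860 = 0.024. At least six stops against none are needed for significance, so the confidence interval will tell more than the test.

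**The case against.** Several objections are fair and limit the point.

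- A reader might infer that withdrawal is the plan's tolerability outcome. It is not: it is one item in a list of secondary safety measures, and no section gives it that label.
- A reader might infer that the harm counts at the first dose and never later. That holds only under the bronchospasm rule. Study Performance and Risks terminate the same subject, in which case a later event would count, and the bronchospasm rule is not confined to later doses.
- A reader might infer that the harm is lost from the trial. It is not. A later bronchospasm meets the adverse-event definition and is compared by type and in aggregate. It triggers a bronchodilator, and rescue use is compared. It may lower compliance, and a 20% fall feeds the study-level stopping rule.
- The power figures rest on assumed rates and on a test that the plan does not contain. Rates of 20% to 40% find no support in the documents: the planning value is a 5% floor for an adverse event, and all six subjects in the preceding single-dose study tolerated both concentrations.

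What remains is narrower. Adverse events and rescue use do not separate a transient episode from one that ended treatment. Compliance is undefined and does not separate missed doses from a mandated stop. Study Performance records reasons for study termination, not for drug stops. Withdrawal is listed as an outcome with no stated analysis on any reading.

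**Conclusion.** The point holds in this limited form. The withdrawal measure is not well defined, because the sections conflict on study status after a 20% FEV₁ fall. It can miss treatment-ending intolerance and it includes unrelated departures, and no listed outcome gives the number in each arm who could not continue the drug. This is a miscount on one secondary safety measure. The documents do not support the view that the trial's safety conclusion would be wrong.

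The size cannot be fixed from the documents. Under retention, the shortfall among these mandated stops is the share 1 − f, whatever the stop rate; the power losses shown are illustrations only. The change is worth making because the replacement outcome is valid however the conflict is settled, bears directly on the stated hypothesis, and is cheap.

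**What to change.** 1. Reconcile the first-dose check, the bronchospasm paragraph, Study Performance, Risks and Stopping criteria, so that study status after a 20% FEV₁ fall is stated once. No view is taken here on which rule is right.
2. In Endpoints, replace study withdrawal as a safety measure with permanent discontinuation of study drug for intolerance. Define it as any stop that the protocol mandates, at any dose, or the subject's own choice because of symptoms, counted whether or not the subject stays in follow-up. Report study withdrawal separately as disposition, with reasons.
3. In Outcomes, add this to the proportions compared by Fisher's exact test, with the difference between arms and its confidence interval.

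The cost is wording in these sections and recording the date and reason of each drug stop. Tracking of study drug containers is already planned under Administration. The downside is one more secondary safety comparison with limited power at 30 per arm, to be read mainly through its confidence interval.

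### At the plan's own 5% floor, 30 subjects per group give a 78.5% chance of seeing at least one adverse event, not the stated minimum of 80%

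*Combined protocol and SAP*

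**What the plan says.** The sample size is set out in the Statistical analysis section of the combined protocol and SAP. The enrolment target is 60 ("We plan to enroll a total of 60 subjects for this study"), split between xylitol and saline "with a goal of 30 subjects in each group".

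The reason given for that size is safety: as a pilot, "it has been primarily powered to detect common adverse events". The premise is "Assuming that the likelihood of a subject experiencing an adverse event is no less than 5"%, and the conclusion drawn from it is that "a sample size of 30 subjects ensures 80% power towards event detection". A parenthesis then defines what power means here: "with a group sample size of 30, the probability of observing at least one adverse event in the group is at least 80"%.

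A second calculation comes later, under Outcomes, and it is introduced as a check on a size already chosen: "To assess the adequacy of these group sample sizes for testing a trend in efficacy, we consider the outcome of log CFU". That check arrives at 17 per group.

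**The concern.** The claim is framed as a lower bound. The rate may be 5% or anything higher, and the detection probability is said never to fall below 80%. That probability rises with the event rate, so the lowest admissible rate, 5%, is the case that decides whether the bound holds. A quick calculation at 5% comes out below 80%.

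The statement carries some weight because it is the only calculation that produces 30 per group; the log CFU calculation needs just 17. In a safety pilot, readers will also use this figure to judge what it means when an event is not seen. If the true rate is 5%, the chance that a group of 30 shows no such event is 21.5%, whereas the plan implies at most 20%.

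**Working it through.** **Inputs**, all from the Statistical analysis section:

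- event probability per subject: p = 0.05, the lowest value the premise allows;
- group size: n = 30;
- stated result: probability of at least one event in the group of 80% or more.

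**The plan's own figure.** With independent subjects who share the same probability, P(at least one event) = 1 − (1 − p)^n. At the plan's values this is 1 − 0.95^30 = 1 − 0.2146 = 0.7854, or 78.5%. The shortfall is 80.0 − 78.5 = 1.5 percentage points.

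**Group size that reaches 80% at a 5% rate.** Solving 0.95^n = 0.20 gives n = ln(0.20)/ln(0.95) = 31.38, so 32 subjects are needed.

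| n per group | 1 − 0.95^n |
|---|---|
| 30 | 78.5% |
| 31 | 79.6% |
| 32 | 80.6% |

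**Event rate that reaches 80% with 30 subjects.** Solving (1 − p)^30 = 0.20 gives p = 1 − 0.20^(1/30) = 0.05223. A rate of 5.22% gives 79.98%, just short, so the threshold rounded upward is 5.23%.

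| Event rate | 1 − (1 − p)^30 |
|---|---|
| 5.0% | 78.5% |
| 5.3% | 80.5% |
| 6% | 84.4% |
| 10% | 95.8% |

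**Other readings.**

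- A Poisson approximation gives 1 − exp(−30 × 0.05) = 1 − exp(−1.5) = 77.7%, which is lower still.
- Pooling both arms gives 1 − 0.95^60 = 95.4%, but the plan's parenthesis refers to a single group.
- Significance level, sidedness and continuity correction do not enter, because this is a detection probability and not a test.

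**The log CFU check, for comparison.** The inputs under Outcomes are a difference of 1.5, an SD of 1.5 and a two-sided two-sample t-test at 0.05. The standardised difference is 1.5/1.5 = 1, and the noncentrality parameter is √(n/2) on 2n − 2 degrees of freedom.

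| n per group | Power |
|---|---|
| 16 | 78.1% |
| 17 | 80.7% |
| 30 | 96.8% |

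The plan's 17 reproduces as the smallest group size that actually reaches 80%. In that calculation the plan did not let a size giving 78.1% stand for 80%.

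**The case against.** The strongest reply is that this is rounding. The figure is within two percentage points of 80%, the difference is two subjects per group, and pairing a round sample size with a round 80% is common in a pilot. Had the plan said approximately 80%, there would be nothing to raise. That much is right. But the plan says the sample size *ensures* the figure and calls it a minimum, and a minimum is false if its worst case falls below it. The log CFU calculation in the same section does hold itself to a strict 80%.

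A second reply is that the bound fails only for rates between 5.00% and about 5.22%, and that the 5% is an assumed floor, less certain than a gap of this size. For adverse events taken together, a rate so close to 5% is implausible: the Adverse events paragraph counts any untoward occurrence regardless of cause, the subjects are inpatients with an exacerbation, and the Risks section expects some cough. This is fair for the aggregate. It carries less force for individual event types, which Outcomes also plans to compare and for which 5% is a relevant rate.

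A third reply is that nothing depends on observing at least one event. The adverse-event comparisons use Fisher's exact test and a Poisson comparison, and the Stopping criteria rest on FEV₁ falls. This stands, and it is why the point is minor.

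The source cited for the calculation is not available here, so whether 30 came from a rounded table cannot be checked. The parenthesis defines the quantity plainly enough that the source would not change the result.

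**Conclusion.** The statement is wrong as written, by a small amount. At the 5% floor the detection probability is 78.5% against a stated minimum of 80%. The gap of 1.5 points is equivalent to two subjects per group (32 against 30), or to a floor of about 5.23% in place of 5%. Above that rate the sentence is true.

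The severity is minor. The finding does not invalidate 30 per group and is not evidence of an undersized trial. The log CFU check is unaffected.

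The result assumes independent subjects with a common event probability, and that all 30 in the group can be assessed for adverse events. The plan gives no dropout allowance for this figure. Purely as an illustration, 29 assessable subjects would give 1 − 0.95^29 = 77.4%, and 28 would give 1 − 0.95^28 = 76.2%.

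**What to change.** Keep enrolment at 60 and restate the parenthesis in the Statistical analysis section along these lines:

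> With 30 subjects per group, the chance that a group shows at least one event is 78.5% for an event with a 5% rate, and 80% or more for events with a rate of 5.3% or higher.

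Amend the preceding sentence to match, so that it no longer says that 30 subjects ensure 80% power from a 5% rate upward.

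The cost is two sentences and a stated figure that is 1.5 points lower. Enrolment, design and analysis do not change. If the sponsor prefers to keep a strict 80% at exactly 5%, the arithmetic calls for 32 per group, or 64 in total, but the finding does not require that.

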Inclusion Criteria: Subjects with CF (medical record evidence of cystic fibrosis transmembrane conductance regulator mutation or sweat chloride test or nasal voltage difference, **and** 1 or more clinical findings of CF), age 12 or greater with an FEV₁ >30% predicted (within the last 14 days) and oxygen saturation \geq 90% on FiO₂ \leq 50%, admitted for an exacerbation, able to provide written informed consent or assent.

Exclusion Criteria: Pregnancy, hemoptysis more than 60 mL within the last 30 days, use of any investigational study drug within the last 30 days, initiation of hypertonic saline within the last 30 days, known intolerance to hypertonic saline, serum creatinine 2 mg/dl or more, active malignancy in the last year, on waiting list for lung transplantation, received a solid organ transplant, lack of FEV₁ data from the last 14 days and previous participation in this study.

Experimental Treatment: Aerosolized 15% xylitol, 5 ml twice a day for 2 weeks using Pari LC nebulizer with Vios compressor, (Pari Inc, Monterey, CA) . Xylitol crystals are

made as food additives by Danisco Cultor, USA. Aerosol solution is sterile, non-pyrogenic, preservative-free solution for inhalation made by UI Pharmaceuticals (Iowa City, IA).

Control Treatment: Hypertonic 7% saline (UIHC pharmacy) 4 ml twice a day for 2 weeks using the same kind of nebulizer.

Screening and Baseline Visit: On the day of admission for exacerbation, informed consent obtained in subjects whose admission spirometry (or spirometry within the last 14 days prior to admit date) shows an FEV₁ >30% predicted. Once consented, subjects will be randomized to either xylitol or saline group as per the randomization code previously generated by the statistician. Demographics, current medications use and the revised CF quality of life questionnaire (CFQ-R) will be completed. Spontaneously expectorated sputum will be collected and processed for cell count and cytokines and quantitative cultures. Blood will be collected for chemistry and liver function tests (LFT). Pregnancy test will be done in women. All medication use during hospitalization will be recorded. Treatment will begin the day after admission for an exacerbation. Results from spirometry that is routinely done twice a week for inpatients will be recorded. All spirometry testing will follow the 2005 American Thoracic Society guidelines.

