The primary outcome is FEV₁ change from baseline. To test for a difference in the mean change between the treatment group and the control group, a two-sample t-test will be conducted. To estimate the difference in the mean change, the equivalent confidence interval procedure will be used. Prior to conducting the test, normality will be assessed for each group based on normal probability plots. If gross departures from normality are observed, a Wilcoxon rank sum test will be performed instead of the t-test. (With group sample sizes of 30, the t-test is fairly robust to departures from normality.)

The same analytical approach will be used to assess differences in the group means for the following variables: the primary outcome of change in respiratory symptom score, and the efficacy outcomes of change in density of colonization (per gram of sputum),

change in sputum cytokines and cell counts, and responses to all Likert-scale questions on the CFQ-R.

To analyze group differences in the efficacy outcome of time to next exacerbation, a time-to-event analysis will be conducted. Kaplan-Meier estimates will be obtained for each survival curve (where failure is defined by exacerbation). To compare the survival distributions, a log rank test will be employed.

To compare the proportion of subjects in each group who have experienced any adverse events, Fisher's exact test will be used. Since certain subjects may experience multiple adverse events, we will also compare the incidence of adverse events in each group. For this comparison, a test will be conducted to contrast the mean number of events in each group, where the two samples of event counts are treated as arising from independent Poisson distributions. To estimate the difference in group proportions and the difference in group means, equivalent confidence interval procedures will be employed.

The preceding inferential procedures will be conducted for individual types of adverse events (e.g., cough, chest tightness, headache), as well as the aggregate of all adverse events. Fisher's exact test will also be used to compare the compliance proportion and the proportion of rescue bronchodilator use in each group.

Since this study is a randomized, controlled clinical trial, we expect the treatment group and the control group to be balanced with respect to factors that could affect the primary

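### The analysis called intention to treat is a dosed-subject set, and the plan contradicts itself on whether subjects with a 20% FEV₁ fall stay in the study and supply a primary outcome

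*Combined protocol and SAP*

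**What the plan says.** **Analysis set.** The Outcomes part of the statistical analysis section defines it in one sentence: "Data from all patients who have received at least one dose of the drug or placebo will be analyzed". The next sentence concludes: "Thus, the analysis will be based on intention to treat". The trial has no placebo; the control is 7% hypertonic saline (Control Treatment).

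**Timing.** The Screening and Baseline Visit section, which describes the day of admission, says: "Once consented, subjects will be randomized to either xylitol or saline group as per the randomization code previously generated by the statistician". Later it says: "Treatment will begin the day after admission for an exacerbation".

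**Subjects with a large fall.** The First dose pre and post spirometry section says: "Subject is excluded from the study if SpO₂ is <89% or FEV₁ declines by 20% or greater from baseline". The paragraph on bronchospasm withholds further study drug after a fall of 20% or more, then adds: "However, they will remain in the study for completion of data collection". Study Performance says: "The subject will undergo a spirometry and if the FEV₁ has declined by 20%, the subject will be terminated from the study". The section on minimizing risks repeats that rule.

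**Primary outcome.** "The primary outcome is FEV₁ change from baseline". Neither Endpoints nor Outcomes says at which time the change is taken. For sputum density, by contrast, Endpoints names Day 14. There is no missing-data rule.

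**The concern.** There are two separate problems.

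The first is the label. When randomization precedes dosing, a set limited to dosed subjects can lose people from either arm after assignment, so it is not an intention-to-treat set.

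The second matters more. FEV₁ change is the primary safety outcome, and an FEV₁ fall is also a reason for removal after randomization. If removal means that no later FEV₁ is collected, whether a subject contributes to the primary comparison depends on that subject's own response to the drug. Sputum, CFQ-R and time-to-event outcomes would be affected in the same way if follow-up ends at removal. As the text stands, whether the worst responders count in the primary test could be settled after the data are seen.

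**Working it through.** **1. The label.** Randomization is at consent on the admission day and the first dose is the day after. A subject can therefore be randomized and never dosed, and the dosed-only rule drops that subject. The documents give no expected number. With a gap of about one day in hospitalized patients it may be small.

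**2. What happens to a subject with an FEV₁ fall of 20%.**

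| Section | Status |
|---|---|
| First dose pre and post spirometry | Excluded from the study |
| Study Performance | Terminated from the study |
| Risks are minimized as follows | Terminated from the study |
| In the event of bronchospasm | No further drug, stays for data collection |
| Outcomes | Analysed, because at least one dose was received |

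The bronchospasm paragraph is not restricted to later doses, so a first-dose reactor could fall under either it or the exclusion rule.

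**3. Does a reactor have a primary value?** This depends on two things that the plan leaves open.

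- Change taken after the first dose: the value exists, because spirometry is repeated after that dose, and the dosed-subject rule includes it.
- Change taken at Day 14, data collection continues: a value can exist.
- Change taken at Day 14, data collection ends on removal: there is no value, and the t-test omits the subject.

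Only the third case turns the primary test into a comparison of those who tolerated the drug.

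**4. Size in the third case.** The documents give no reactor rate and no FEV₁ SD, so the following rests on assumptions. Let tolerators have the same mean change in both arms, and let reactors differ from them by a gap of 20 to 30 points (% of baseline) in the analysed change. Then

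hidden mean difference = (xylitol reactor rate − saline reactor rate) × gap.

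| Assumed rates, xylitol vs saline | Gap 20 | Gap 30 |
|---|---|---|
| 3.3% vs 0% (1 of 30 vs none) | 0.7 | 1.0 |
| 10% vs 5% | 1.0 | 1.5 |
| 10% vs 0% | 2.0 | 3.0 |
| 20% vs 5% | 3.0 | 4.5 |
| Equal rates | 0 | 0 |

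The gap must apply to the change actually analysed. If only half of an acute fall persisted to Day 14 (gap 10 to 15), 10% vs 0% would hide 0.10 × 10 = 1.0 to 0.10 × 15 = 1.5 points.

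**5. Bias or lost power?** The plan's figure of 17 per group for log CFU reproduces: the standardized effect is 1.5/1.5 = 1.0, and the exact two-sided t calculation gives 16.7, so 17, with power 0.807. With all 30 per group, power is 0.968. If 10% of each arm gave no usable data (n = 27) it would be 0.950, and with 20% lost (n = 24) it would be 0.924. The FEV₁ difference detectable with 80% power moves from 0.74 SD to 0.78 and 0.83 SD. These losses are modest, so the problem is mainly bias, which a larger sample would not remove.

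**The case against.** The strongest reply is that the analysis rule already covers reactors: they have received a dose, their post-dose FEV₁ is measured, and one paragraph keeps subjects with such a fall under observation. Routine inpatient spirometry twice a week is also recorded, and nothing states that recording ends on exclusion. This stands. A reader might infer that the primary comparison is made only among those who tolerated the drug, but the documents do not establish that. What remains is that membership of an analysis set does not supply an outcome value, and the plan does not say where one would come from.

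A reader might also infer that harm would go unseen. That is not supported either. Withdrawal is a listed safety assessment, terminations and their reasons are tracked, adverse events are compared by arm, and three subjects with 20% falls, if all on xylitol, close recruitment under Stopping criteria. At an assumed 10% rate, the chance of at least one reactor among 30 xylitol subjects is 1 − 0.9^30 = 0.958, with 30 × 0.10 = 3 expected. Only the mean-FEV₁ comparison could miss them, and the plan says that the study is powered mainly to detect common adverse events.

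Finally, the first-dose test applies to both arms, and equal reactor rates give no bias in the mean difference. This is correct, but equality cannot be presumed. Known intolerance to hypertonic saline is an exclusion criterion with no xylitol counterpart, and the Risks section foresees bronchospasm with xylitol in subjects whose hyperresponsiveness was not previously known.

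**Conclusion.** The concern holds in a limited form. Two parts rest on the text alone: the intention-to-treat label is wrong for a dosed-only set when randomization comes first, and the sections on subjects with a 20% fall contradict one another. The absence of a primary time point and of a missing-data rule is equally plain.

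The bias is conditional. It needs removal to end data collection, the primary change to be taken at Day 14 or another later visit, and reactor rates to differ by arm. Its size cannot be taken from the documents. Under the stated assumptions it runs from 0 with equal rates, through 2 to 3 points at 10% vs 0%, to 4.5 points in the most extreme case shown. It would be smaller if acute falls resolve before the analysed visit. The point concerns the primary between-group estimate and the efficacy comparisons; the adverse-event, withdrawal and stopping counts would still register reactors.

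**What to change.** 1. Reconcile First dose pre and post spirometry, In the event of bronchospasm, Study Performance and the risk-minimization text so that stopping study drug is a separate event from leaving the study. The criterion for giving no further drug is not at issue here and stays as it is. Continue Day 14 and phone data collection for all randomized subjects.
2. In Outcomes, analyse efficacy in all randomized subjects as randomized. Name the dosed set as the safety set, with first-dose reactors explicitly included, and do not call it intention to treat.
3. Fix the time point of the primary FEV₁ change, and state how FEV₁ from subjects who stopped drug is used and how missing values are handled.
4. Report by arm, in all dosed subjects, the first-dose FEV₁ change and the proportion with a fall of 20% or more.
5. Where a reactor has no later FEV₁, use the post-first-dose value only in a sensitivity analysis. A reading taken 15 to 30 minutes after a dose and a Day 14 reading are different quantities and should not be mixed in the main mean.
6. Replace the word placebo with hypertonic saline.

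The cost is protocol and SAP wording, a little more analysis, and a few extra visits and calls. At assumed reactor rates of 5% to 10%, that is 30 × 0.05 = 1.5 to 30 × 0.10 = 3 subjects per arm, plus any who are randomized but never dosed.
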